5.3.1 Adverse Event Reporting Period

Investigators will seek information on adverse events at each patient contact. All adverse events, whether reported by the patient or noted by study personnel, will be recorded in the patient's medical record and on the Adverse Event eCRF.

After informed consent has been obtained but prior to randomization (randomized arms) or initiation of study drug (non-randomized arm), only serious adverse events caused by a protocol-mandated intervention (e.g., invasive procedures such as biopsies, discontinuation of medications) should be reported (see Section 5.4.2 for instructions for reporting serious adverse events).

After randomization (randomized arms) or initiation of study drug (non-randomized arm), all adverse events will be reported until the patient completes his or her last study visit (i.e., 24 weeks after the last dose of study drug). After this period, the investigator should report any serious adverse events that are believed to be related to prior study drug treatment (see Section 5.6).

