5.3.2 Eliciting Adverse Event Information

A consistent methodology of non-directive questioning should be adopted for eliciting adverse event information at all patient evaluation timepoints. Examples of non-directive questions include the following:

"How have you felt since your last clinic visit?"

"Have you had any new or changed health problems since you were last here?"

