6.6 SAFETY ANALYSES

The safety analyses population will be based on all enrolled patients grouped according to the actual treatment received. For Arm C patients, all safety data reported up to the day prior to switching will be included in the 'control arm' safety summaries, and all safety data reported on or after the date of switching to active treatment will be reported separately.

Safety will be assessed through descriptive summaries of adverse events, laboratory test results (serum chemistry and hematology, including complete blood count with differential), ECGs, vital signs, and antibodies to emicizumab and FVIII.

To evaluate the overall safety of prophylactic emicizumab compared to no prophylaxis, the incidence of adverse events will be summarized and presented by System Organ Class mapped term, appropriate thesaurus level, and toxicity grade for each treatment arm.

For clinical laboratory data, summary statistics will be presented by treatment arm. In addition, shift tables describing changes from baseline will be presented using the WHO toxicity grading scale.

Data on the impact of immunogenicity (anti-emicizumab antibodies) on safety, efficacy, and/or clinical pharmacology and PK will be summarized adopting standard language/terminology (Shankar et al. 2014).

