Appendix 1 Schedule of Assessments (cont.)

Schedule of Assessments—Arm C (Screening to Switch to Emicizumab)								
	Screen- ing	Wk 1	Wk 5	Wk 9	Wk 13	Wk 17	Wk 21	Daily/ weekly ^a
Informed consent ^c	x							
Inclusion/exclusion criteria	x							
Medical history and demographics ^d	x							
Physical examination (including weight) ^e	x	x						
Vital signs (including weight) ^f	x	x ^f	x	x	x	x	x	
Height	x							
Serum pregnancy test ^h	x							
HJHS ^g	x							
Concomitant medications ⁱ	x	x	x	x	x	x	x	
ECG ^j	x	x ^j						
Safety laboratory assessments ^h	x ^h	x						
Anti-FVIII antibodies ^k	x							
Bleed/injection questionnaire ^m								x
Bleed/injection data review ⁿ		x	x	x	x	x	x	
Adverse events ^o		x	x	x	x	x	x	
HRQoL and health status ^q		x			x			
Activity measure (optional) ^u		x						
PD biomarkers assessment ^s		x						
Bone biomarkers (fasted) ^t		x						
RCR blood DNA sample (optional) ^w			x					

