Appendix 1 Schedule of Assessments (cont.)

Schedule of Assessments—Arm C (Continued, at Time of Switch to Emicizumab)																		
	Wk 25	Wk 26	Wk 27	Wk 28	Wk 29	Wk 31	Wk 33	Wk 37	Wk 41	Wk 45	Wk 49	Every 8 Wks from Wk 57	Wk 73	Every 12 Wks from Wk 85	Every 24 Wks from Wk 97	Daily/ weekly ^a	Study Compl- etion/ ET	Safety F/U Visit ^b
Adverse events ^o	x	x	x	x	x	x	x	x	x	x	x	x	x	x	x		x	x
IMP management ^p	x	x	x	x	x	x	x	x	x	x	x	x	x	x	x		x	
HRQoL and health status ^q	x							x			x		x		x ^q		x	
PK assessment ^r	x	x	x	x	x	x	x	x	x	x	x	x	x	x	x		x	x
PD biomarkers ^s	x	x	x	x	x	x	x	x	x	x	x	x	x	x	x		x	x
Bone biomarkers (fasted) ^t	x							x			x		x		x		x	
Activity measure (optional) ^u	x										x							

BMQ=bleed and medication questionnaire; eCRF=electronic Case Report Form; EQ-5D-5L=EuroQoL Five-Dimension-Five Levels Questionnaire; ET=early termination; F/U=follow-up; FVIII=factor VIII; HRQoL=health-related quality of life; HJHS=Hemophilia Joint Health Score; IMP=investigational medicinal product, PD=pharmacodynamic; PK=pharmacokinetic; RCR=Roche Clinical Repository; SQ-ISHI=Satisfaction Questionnaire–Intravenous Subcutaneous Hemophilia Injection; wk=Week.

Notes: The maximum allowable time between screening and enrollment is 6 weeks; if the elapsed time between screening and enrollment is more than 6 weeks, screening must be repeated. All assessments should be performed within ± 2 days of the scheduled visit for the first 12 weeks and for Weeks 25–37 for Arm C patients who switch over, then ± 7 days thereafter. Clinic visits should coincide with the day of emicizumab dosing, and on those days the dose should be administered after blood draws and other assessments are conducted. Unscheduled assessments may be performed at the discretion of the investigator and as clinically indicated. Except for the bleed/injection questionnaire, HRQoL, and health status, all other patient data will be collected during office or nurse visits. Evaluation at Weeks 25 or 49 will occur after a full 24 or 48 weeks in the study. Study completion evaluation occurs when a patient discontinues emicizumab or transitions into another study.

^a Patients will complete the Bleed/Medication Questionnaire at least weekly and at the time of a bleed, or when they take a hemophilia-related medication (including emicizumab). Arm B patients should indicate at least weekly whether or not they had a bleed.

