#### **Safety Analysis**

The safety analyses population will be based on all enrolled patients grouped according to the actual treatment received. For Arm C patients, all safety data reported up to the day prior to switching will be included in the 'control arm' safety summaries, and all safety data reported on or after the date of switching to active treatment will be reported separately.

Safety will be assessed through descriptive summaries of adverse events, laboratory test results (serum chemistry and hematology, including complete blood count with differential), ECGs, vital signs, and antibodies to emicizumab and FVIII.

To evaluate the overall safety of prophylactic emicizumab compared to no prophylaxis, the incidence of adverse events will be summarized and presented by System Organ Class mapped term, appropriate thesaurus level, and toxicity grade for each treatment arm.

For clinical laboratory data, summary statistics will be presented by treatment arm. In addition, shift tables describing changes from baseline will be presented using the WHO toxicity grading scale.

Data on the impact of immunogenicity (anti-emicizumab antibodies) on safety, efficacy, and/or clinical pharmacology and PK will be summarized adopting standard language/terminology.

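### Protocol 6.6 splits Arm C adverse events by report date rather than onset, so events that began on no prophylaxis but first surface at the Week 25 switch visit can leave the control summaries

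*Protocol*

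**What the plan says.** Protocol 6.6 bases the safety population on enrolled patients "grouped according to the actual treatment received". It then divides Arm C in time. Data reported before the switch date belong to the control arm, and for the rest "all safety data reported on or after the date of switching to active treatment will be reported separately". The Protocol synopsis carries the same rule, as does the synopsis reprinted in SAP Appendix 1 ("all safety data reported up to the day prior to switching will be included in the 'control arm' safety summaries").

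On collection, Protocol 5.3.1 states: "Investigators will seek information on adverse events at each patient contact". An example question in 5.3.2 looks back over the interval between visits: "How have you felt since your last clinic visit". In Protocol Appendix 1, the Arm C adverse-event row is marked at Weeks 1, 5, 9, 13, 17 and 21, and next at Week 25, the first column of the table that starts at the switch. For visits on dosing days the appendix notes add that "on those days the dose should be administered after blood draws and other assessments are conducted".

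The SAP body says little on this. SAP 4.1 analyses the two Arm C periods separately and includes the post-switch period in the All Emicizumab outputs, which cover safety. SAP 4.2.5 admits Arm C switchers to SAF2. SAP 4.7.2 describes the adverse-event summaries by treatment arm and gives no rule for assigning an event to a period.

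**The concern.** When an event is reported and when it began are different dates, and they differ most for non-serious events that a patient mentions only when asked. In Arm C the first scheduled enquiry after Week 21 falls on the switch date itself. What is elicited there began before the patient had received any emicizumab, yet it is reported on the date from which the rule stops counting data as control.

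The safety objective compares emicizumab with no prophylaxis, and Arm C before the switch is the only no-prophylaxis group, with 17 patients planned. The literal rule takes events out of that small group and places them in the Arm C emicizumab-period outputs. Both shifts work against emicizumab. The rule also conflicts with the principle of grouping by treatment received in the same paragraph.

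**Working it through.** The only safety figure in the plan is the probability of seeing at least one adverse event with 1% true incidence among 108 to 128 emicizumab patients, given as 0.66 to 0.72 (Protocol 6.1). It reproduces: 1 − 0.99^108 = 0.662 and 1 − 0.99^128 = 0.724. The present point does not affect it.

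**Inputs from the documents**
- Control period in Arm C: 24 weeks = 168 days (Protocol 3.1).
- Last scheduled control enquiry at Week 21, next at Week 25 (Protocol Appendix 1): 4 weeks = 28 days.
- Visit windows: ±7 days at Week 21, and ±2 days at Week 25 for patients who switch (Appendix 1 notes).
- Planned control arm: 17 patients (Protocol 6.1).

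**Step 1: share of control time exposed.** This is the interval between the two visits divided by the control period.
- Nominal: 28/168 = 16.7%.
- Week 21 late by 7 days and Week 25 early by 2: (28 − 9)/(168 − 2) = 19/166 = 11.4%.
- Week 21 early by 7 days and Week 25 late by 2: (28 + 9)/(168 + 2) = 37/170 = 21.8%.
- In patient-weeks: 17 × 4 = 68 of 17 × 24 = 408.

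**Step 2: from time to events.** With a constant onset rate, the share of control events moved is 16.7% × f, where f is the fraction of events in that interval that first surface at the visit. The documents do not give f. At f = 1 the share is 16.7%, at f = 0.5 it is 8.3%, and at f = 0.25 it is 4.2%.

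**Step 3: what this means in counts.** The documents give no adverse-event rate, so the rates below are assumptions. All rows use f = 1, the ceiling. Control time is 17 × 168/365.25 = 7.82 patient-years, and the exposed part is 17 × 28/365.25 = 1.30 patient-years. Patients with at least one event are 17 × (1 − exp(−rate × days/365.25)), with 168 days by onset and 140 days by report date.

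| Assumed events per patient-year | Control events by onset | Moved, at most | Patients with ≥1 event, by onset | Same, by report date |
|---|---|---|---|---|
| 1 | 7.8 | 1.3 | 6.3 | 5.4 |
| 2 | 15.6 | 2.6 | 10.2 | 9.1 |
| 4 | 31.3 | 5.2 | 14.3 | 13.3 |
| 6 | 46.9 | 7.8 | 15.9 | 15.3 |

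Patient-level incidence changes proportionally less than the event count, because a patient with an earlier control event still counts. At 4 events per patient-year it falls from 14.3 to 13.3 patients, about 7%.

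**Step 4: is the rule overridden elsewhere?** SAP 4.7.2 is silent on onset. SAP 2.3.1.1 ends Arm C's first efficacy period on the day before the first emicizumab dose, so bleed data have a period anchored to treatment. No equivalent rule is written for adverse events.

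**The case against.** The strongest reply is that *reported* is a loose verb. The sentence covers all safety data, including laboratory values, ECGs and vital signs, and it follows directly on grouping by treatment received. Protocol 3.1 says adverse events are captured as they occur. SAP 4.1 describes the two Arm C periods by treatment and the All Emicizumab outputs as data collected under emicizumab; a pre-dose enquiry on the switch day is not that. The SAP's repetition of the rule is also weak support, since its reprinted synopsis comes from an earlier protocol version (study length 2 years, against 6 in the current protocol). This makes it plausible that onset was intended. It does not supply the rule: the current Protocol 6.6 says reported, no text says onset, and two programmers could produce different tables from it.

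Three limits on the consequence stand. Serious events and events of special interest must reach the sponsor within 24 hours of the investigator learning of them (Protocol 5.4). Enquiry is made at every contact, not only at scheduled visits. Non-serious bleeds consistent with the pre-study disease are not adverse events at all (Protocol 5.2.1).

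A reader might infer more than the documents support:
- That a tenth to a sixth of control events will be misattributed. This would need 60% to 100% of events to wait for the visit, and no document gives that share.
- That Arms A and B have no period cut. SAP 4.1 reports data after up-titration separately there too, although that split lies between two emicizumab doses and never between control and drug.
- That moved events enter Arms A or B. Protocol 6.6 keeps post-switch Arm C data apart; they join an emicizumab total only through the All Emicizumab and SAF2 outputs.

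**Conclusion.** The point holds as a defect in a written rule. Taken literally, Protocol 6.6 attributes to the Arm C emicizumab period some non-serious adverse events that began on no prophylaxis, and nothing in the SAP corrects this. The exposed share of control adverse-event time is a ceiling, whether taken at its nominal value or with visit windows. It rests on a constant onset rate and on every event in the last interval waiting for the Week 25 visit, so the actual share of events moved cannot be fixed from the documents. The direction is against emicizumab. Because safety is summarised descriptively, no test, primary result or sample-size statement changes. It is still worth correcting: the control group is small, and an unambiguous rule is cheap.

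**What to change.** In Protocol 6.6, the matching synopsis text and SAP 4.7.2, replace assignment by report date with assignment by adverse-event onset date relative to the first emicizumab dose:
- Onset before the date of the first dose counts as control, whenever the event is reported.
- Events elicited at the pre-dose Week 25 enquiry or examination count as control.
- Any other onset on or after the first-dose date counts as the emicizumab period.
- State a convention for partial start dates.

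Protocol 5.3.5.2 already refers to a starting date for adverse events, so the core rule appears to need no new data. It should not depend on time of onset or on the date a grade worsened unless the eCRF records them. The documents do not show that onset time is collected, and for persistent events Protocol 5.3.5.4 describes initial and most extreme severity, with a date only for becoming serious. The cost is a short text change and the matching derivation in the analysis programs.

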6.7 PHARMACOKINETIC ANALYSES

For all patients, pre-dose (trough) plasma concentrations of emicizumab will be presented descriptively by treatment group, including arithmetic and geometric means, median, range, standard deviations, and coefficients of variation.

Nonlinear mixed effects modeling will be used to analyze the dose-concentration-time data of emicizumab following SC administration. Population PK parameters, such as clearance and volume of distribution, will be estimated, and the influence of various covariates, such as age, gender, and body weight, on these parameters will be investigated graphically. Secondary PK parameters, such as AUC, will be derived from individual post-hoc predictions. Data may be pooled with data from other studies. These analyses will be reported in a dedicated report.

6.8 EXPLORATORY ANALYSES

Summary statistics of the number of work/school days missed and days hospitalized will be presented by treatment arm. Summary statistics will also be presented for the SQ-ISHI and emicizumab Preference Survey. PD parameters (e.g., aPTT, parameters derived from thrombin generation, FVIII activity) and markers related to bone and joint health will be presented using summary statistics, including arithmetic and geometric means, median, range, standard deviations, and coefficients of variation.

For the activity assessment all enrolled subjects that contribute reliable activity data (i.e., at least 8 valid days) will be analyzed. There will be no imputation of missing data. Subjects will be grouped according to the treatment regimen to which they are assigned in the main study. Because of the exploratory nature of the study, there will be no type-1 error control for multiplicity. Enrollment, discontinuations, protocol violations/deviations, and duration of activity monitoring follow-up will be summarized. Demographic and baseline characteristics, such as age, sex, race/ethnicity, and weight will be summarized using descriptive statistics. Relative change is defined as

$$100 \times (DSC_{\text{Week } n} - DSC_{\text{baseline}}) / DSC_{\text{baseline}}$$

Relative change from baseline at Week 25 or 49 in mean DSC and activity counts (total, mean, and peak) will be calculated within each treatment group provided the patient has reported data on at least 8 days within the 14 day observation period. Subject-level averages at each timepoint will be presented via dot-plots and descriptive statistics by treatment group.

The main comparisons will be within-patient changes, calculated within each treatment group. Within the control arm, where patients are expected to switch to emicizumab prophylaxis treatment at 24 weeks, an additional comparison of the relative change from Week 25 to Week 49 will be performed.

Formal statistical modeling may be performed as appropriate. Such analysis will be based on between-treatment comparisons of the change in activity from baseline to Week 25 between patients receiving emicizumab prophylaxis (Arms A or B) versus no prophylaxis (Arm C).

6.9 INTERIM ANALYSIS

No interim analysis for efficacy is planned.

7. DATA COLLECTION AND MANAGEMENT

7.1 DATA QUALITY ASSURANCE

The Sponsor will be responsible for data management of this study, including quality checking of the data. Data entered manually will be collected via EDC through use of eCRFs. Sites will be responsible for data entry into the EDC system. In the event of discrepant data, the Sponsor will request data clarification from the sites, which the sites will resolve electronically in the EDC system.

The Sponsor will produce an EDC Study Specification document that describes the quality checking to be performed on the data. Data will be sent directly to the Sponsor, using the Sponsor's standard procedures to handle and process the electronic transfer of these data.

eCRFs and correction documentation will be maintained in the EDC system's audit trail. System backups for data stored by the Sponsor and records retention for the study data will be consistent with the Sponsor's standard procedures.

ActiGraph will be responsible for data management of the activity monitoring, including quality checking of the data. Sites will be responsible for setting up (initializing) activity monitors and downloading data from the monitors using ActiGraph's CentrePoint software, a web-based physical activity monitoring logistics platform. The CentrePoint solution consists of two components: a client-side software application (ActiSync), which directly interacts with the monitors on each site's computer and remotely distributed storage and processing servers hosted by Amazon® Web Services and Microsoft® Azure cloud computing platforms located in the United States. ActiGraph is in the process of completing the implementation of full server-side audit logging. Once complete, the CentrePoint solution will be fully CFR Part 11 compliant.

Actigraph will produce a Data Quality Plan that describes the quality checking to be performed on the data. Data will be transmitted to the Sponsor using the Sponsor's standard procedures to handle and process the electronic transfer of these data

7.2 ELECTRONIC CASE REPORT FORMS

eCRFs are to be completed through use of a Sponsor-designated EDC system. Sites will receive training and have access to a manual for appropriate eCRF completion. eCRFs will be submitted electronically to the Sponsor and should be handled in accordance with instructions from the Sponsor.

All eCRFs should be completed by designated, trained site staff. eCRFs should be reviewed and electronically signed and dated by the investigator or a designee.

At the end of the study, the investigator will receive patient data for his or her site in a readable format on a compact disc that must be kept with the study records. Acknowledgement of receipt of the compact disc is required.

7.3 ELECTRONIC PATIENT-REPORTED OUTCOME DATA

PRO data will be collected electronically with use of electronic devices provided by a vendor. The electronic device is designed for entry of data in a way that is attributable, secure, and accurate, in compliance with U.S. Food and Drug Administration (FDA) regulations for electronic records (21 Code of Federal Regulations, Part 11). The data will be transmitted electronically in real-time to a centralized secure database at the vendor. The data from the devices are available for view access only via secure access to a Web portal provided by the vendor. Only identified and trained users may view the data, and their actions become part of the audit trail. The Sponsor will have view access only. Regular data transfers will occur from the centralized database at the vendor to the database at the Sponsor. The Sponsor will receive all data entered by patients on the devices and all relevant study documentation.

Once the study is complete, the data, audit trail, and study and system documentation will be archived. The investigator will receive patient data for the site in both human- and machine-readable formats on an archival-quality compact disc that must be kept with the study records as source data. Acknowledgement of receipt of the compact disc is required. In addition, the Sponsor will receive all patient data in a machine-readable format on a compact disc.

7.4 SOURCE DATA DOCUMENTATION

Study monitors will perform ongoing source data verification to confirm that critical protocol data (i.e., source data) entered into the eCRFs by authorized site personnel are accurate, complete, and verifiable from source documents.

Source documents (paper or electronic) are those in which patient data are recorded and documented for the first time. They include but are not limited to hospital records, clinical and office charts, laboratory notes, memoranda, PROs, evaluation checklists, pharmacy dispensing records, recorded data from automated instruments, copies of transcriptions that are certified after verification as being accurate and complete, microfiche, photographic negatives, microfilm or magnetic media, X-rays, patient files, and records kept at pharmacies, laboratories, and medico-technical departments involved in a clinical study.

Before study initiation, the types of source documents that are to be generated will be clearly defined in the Trial Monitoring Plan. This includes any protocol data to be entered directly into the eCRFs (i.e., no prior written or electronic record of the data) and considered source data.

Source documents that are required to verify the validity and completeness of data entered into the eCRFs must not be obliterated or destroyed and must be retained per the policy for retention of records described in Section 7.6.

To facilitate source data verification, the investigators and institutions must provide the Sponsor direct access to applicable source documents and reports for study-related monitoring, Sponsor audits, and IRB/EC review. The study site must also allow inspection by applicable health authorities.

The entire activity data collection, transmission, and analysis process is 21 CFR Part 11 compliant and includes a complete audit trail. The “source data” from ActiGraph will consist of the raw data, the epoch data (counts), and steps. Derived endpoints (such as calories or any other measure that is derived from raw, epoch, or steps data is not considered source data. ActiGraph will maintain all of the data in multiple redundant data centers hosted on the Amazon Web Services platform. ActiGraph will provide this information as needed for audits by Roche and/or appropriate regulatory agencies.

